8.9.5 ANTI-PEGCETACOPLAN AND ANTI-PEG ANTIBODIES

The proportion of patients with positive anti-drug antibodies (ADA) results during the study will be summarized at each visit for the Safety and PK set. Neutralizing antibodies will also be summarized for patients from the Safety set who had positive ADA results.

The proportion of patients with ADA results by category (as outlined below) will be summarized.

- Patients with treatment emergent ADA: any patient negative for ADA at baseline and positive at any post-baseline samples.
- Patients with treatment boosted ADA: any patient positive for ADA at baseline and with a measurable titer at any post baseline sample if the baseline titer was not reportable or with an increase in titer by 4-fold if the baseline titer was reportable.

ADA titers and fold-increases overall and of the maximum titer of each patient will be summarized descriptively with medians, interquartile range (Q1 and Q3) for treatment-emergent, and treatment-boosted ADA, respectively.

ADA will also be listed.

8.9.6 **DEATHS**

The proportion of patients who died will be summarized by cause of death.

Deaths will also be listed.

9. INTERIM AND FINAL ANALYSIS

No interim analysis will be conducted.

The final analysis is planned to be performed when all patients have completed the End of Study visit (Week 24) or Early Termination visit in case of early discontinuation.

10. DEVIATIONS FROM ANALYSIS AS DESCRIBED IN THE PROTOCOL

- The analysis of target medical events has been introduced to the analysis. This is a new analysis not mentioned in the protocol. The Adverse Event of Special Interest is usually defined prospectively. The alternative term "Target Medical Event" is used to avoid any confusion created by the use of a term associated in normal terminology to a prospective definition.
- The administrative interim analysis required to be conducted by study Protocol Sobi.PEGCET-201 when at least 10 patients have completed 12 weeks of treatment (or have been withdrawn) for informing about future development program will not be conducted. The rationale is that its purpose is future planning of the TA-TMA development program. The Sponsor determined that the planned interim analysis would not provide sufficiently different information from those of the final analysis to provide extra guidance and that there was no need to obtain earlier information for development program planning. The underlying reason is that this provision was thought for the event of a slow recruitment creating a long lead time while the latest study patients were recruited during which development design and interactions with Authorities benefiting for the interim analysis results would need to be conducted. In the actual conduct of the study, the end of the study was a rapid recruitment period (last 5 patients recruited in 5.5 months, of which last 3 patients recruited in about 12 weeks) rendering futile the conduct of the interim analysis as compared to the expected date of the final analysis.

Page 32 of 39

11. PROGRAMMING SPECIFICATIONS

All outputs will be produced using SAS version 9.4 or a later version.

The margins should be at least 1.50 inches for the binding (top) edge and 1.0 inches for all others. Courier New 8-point bold font will be used for all outputs. TLFs will be produced in "rtf", "doc(x)" and "pdf" format in landscape layout. Outputs will be delivered as three files in PDF format: one for all the tables, one for all the listings, and one for all the figures.

In the top left portion of each output, the protocol number will be presented. On the next line, an output number followed by the title of the output and population information will be displayed. Horizontal lines will appear after the column heading of the output. Footnotes will be put under the main body of text at the bottom of the page. All abbreviations used in the output will be given in the footnote. For all tables reporting percentages, the denominator used for percentage calculation will be described either in the body of the table or in a footnote. The source listing number will be displayed for all tables. The SAS program name and programmer ID will appear at the bottom left corner in a string, and the page number will appear in the bottom right corner of each output. The date and time of creation of the output will appear at the top right, just above the page number. Additionally, the following information should be produced by the SAS program and displayed in each output: the sponsor's name, the database lock date or data snapshot date, the cut-off date for analysis (if applicable), and the name of the program output and its location.

Any date information in the listing will use the date9. Format, for example, 07MAY2002.

Example:

Swedish Orphan Biovitrum AB Sobi.PEGCET-201

01DEC2018 11:51 Page X of Y

Listing XXX
Title
(Population)

Source: Listing Number Data set: ADXX

Generated by: \\ PEGCET-201_XXX_XXX.sas (Programmer ID: XX) Final/Draft version
Output: \\ PEGCET-201_XXX_XXX_201812011437 Analysis Cut-off: 15SEP2018 Database Lock: 01OCT2018

The list of TFLs is given in the section below. Shells for unique tables and listings are provided in a separate Mock-Up TFLs document.

12. LIST OF TABLES, LISTINGS, AND FIGURES

The TFLs for this study are presented in a separate document (PEGCET-201 Mock TFLs).

Page 33 of 39

13. APPENDICES

13.1 APPENDIX I. DERIVATION RULES FOR CLINICAL RESPONSE

eCRF forms: Platelet or PRBC Transfusion form, Central laboratory sampling form, Baseline TA-TMA form, Clinical Response Evaluation form,

```
Programming note: If central lab values not available, use local lab values reported on the clinical response evaluation form
Improvement in laboratory markers
IF [(LDH < 1.5 x ULN) AND (Platelet count ≥ 50*10^9/L (50 000/mm^3)) AND
               ((Any blood transfusions performed=No) OR
               ((Any blood transfusions performed=Yes) AND (Type of blood transfusion=PRBC OR
               Type of blood transfusion=Platelet) AND (Date of blood sample taken> Date of last platelet transfusion + 7 days)))]
THEN lab markers response =1 ELSE lab markers response=0
Renal response
IF (Has the patient any sign/symptom of kidney dysfunction=Yes) THEN DO
               IF [(((creatinine_baseline - creatinine)/creatinine_baseline) > 0.4)
               ((creatinine_baseline > ULN mg/dL (abnormal high)) AND (creatinine <= ULN mg/dL (normal))
               OR
               (discontinuation of renal replacement therapy=Yes)
               (((rUPCR_baseline - rUPCR)/ rUPCR_baseline) ≥ 0.5)]
               THEN renal response =1 ELSE renal response=0
END
ELSE renal response=0
Pulmonary response
IF (Has the patient any sign/symptom of lung dysfunction=Yes ) THEN DO
               IF [(Absence of positive pressure ventilation =Yes)
                (Absence of invasive ventilator support=Yes)]
               THEN pulmonary response =1 ELSE pulmonary response=0
END
ELSE Pulmonary response=0
Gastrointestinal (GI)
IF (Has the patient a biopsy-proven GI involvement of TA-TMA=Yes) THEN DO
               IF [(Presence of nausea, vomiting or anorexia attributed to TA-TMA=No)
               ((Stool output: in mL/day < 500 mL/day) OR (Stool output: number of episodes/day< 3 episodes/day))]
THEN GI response=1 ELSE GI response=0
ELSE Gastrointestinal response =0
Cardiovascular response
IF (Has the patient any sign/symptom of Cardiovascular dysfunction=Yes) THEN DO
               ((Has the patient a diagnosis of pulmonary hypertension = Yes) AND (Is pulmonary hypertension present=No))
               [((pre-antihypertensive therapy diastolic blood pressure ≥ 90 mmHg) OR
               (pre-antihypertensive therapy systolic blood pressure ≥ 140 mmHg) OR

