### Improvement in laboratory markers:

- LDH < 1.5 x ULN and
- Platelet count  $\geq 50~000/\text{mm}^3$  without transfusion support during the prior 7 days.

AND in patients with signs or symptoms of organ dysfunction at baseline, in addition to the above laboratory markers, at least 1 of the following clinical criteria needs to be fulfilled, depending on the organ/system involved at baseline as described in Section 6.5.1 (without appearance of new signs or symptoms of organ dysfunction in other organs not present at baseline):

- Renal response requires > 40 % reduction in creatinine, or normalization of creatinine, or discontinuation of renal replacement therapy, or  $\ge 50$  % reduction from baseline in rUPCR.
- **Pulmonary response** requires extubation and discontinuation of positive pressure ventilation.
- o **GI response** applicable only to patients with biopsy-proven GI TA-TMA and requires improvement in GI function as determined by the MAGIC criteria (no or intermittent nausea, vomiting or anorexia attributed to TA-TMA for upper GI; stool output/day for lower GI as follows: < 500 mL/day or < 3 episodes/day) [21].
- Neurological response requires improvement in reversible neurological conditions (e.g., cessation of seizures or controlled under medication, resolution of mental alteration; residual radiologic signs are acceptable without clinical symptomatology), or stabilization of irreversible neurological conditions (e.g., stability of neurological deficits following stroke without further deterioration or subsequent strokes).
- Freedom from transfusion requires absence of platelet or PRBC transfusions attributed to TA-TMA during the prior 7 days (only applicable if patient was undergoing platelet or PRBC transfusion at baseline).
- Cardiovascular response requires resolution of pulmonary hypertension (may receive anti-pulmonary hypertension medications if still on maintenance therapy), or hypertension control on no more than 2 medications excluding diuretics (applicable only to patients with severe hypertension at baseline).
- Serositis response requires no evidence of clinically significant pericardial or pleural effusion requiring surgical therapy (e.g., pericardiocentesis/thoracocentesis).

Patients meeting intercurrent events, including use of prohibited medication or study withdrawal before Week 24, will be considered as failures/nonresponders.

[figure not shown]

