### 6.1.2.1 Clinical worsening

Clinical worsening will be defined as active laboratory TA-TMA as per Inclusion Criterion #3 (see Section 6.3.1) and 3 of the 5 organ injuries listed below:

Confidential Page 33 of 89

- Clinical Study No: Sobi.PEGCET-201
- a. Kidney: requirement of renal replacement therapy after initial TA-TMA control, sustained (> 7 days) and attributable to TA-TMA.
- b. Lungs: requirement of sustained (> 7 days) positive pressure ventilation, and attributable to TA-TMA.
- c. Cardiovascular: uncontrolled severe hypertension with > 2 medications (excluding diuretics), and attributable to TA-TMA.
- d. CNS: uncontrolled seizures under medication attributable to posterior reversible encephalopathy syndrome or to hypertension resulting from TA-TMA.
- e. GI tract: clinically significant GI bleeding requiring ≥ 20 mL/kg/day of PRBC transfusion daily for at least 7 days.

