# Baseline, efficacy, safety, pharmacokinetic, pharmacodynamic and pharmacogenetics assessments

# 6.5.1 Medical history

Medical history will be recorded at screening. Investigators should document the occurrence, signs, and symptoms of the patient's preexisting conditions, including all prior significant illnesses, up to and including 1 year before enrollment in the study. Additional preexisting conditions that started before and are ongoing at the date of enrollment are to be regarded as current medical conditions. Medical history will include alcohol consumption and smoking history, if applicable.

Information about HSCT and related complications will be also collected, including underlying disease diagnosis; donor type; HLA mismatch; stem cell source; type and start date of conditioning regimen; conditioning medications; date of transplant; transplant manipulation; donor chimerism; date of confirmed engraftment; GVHD date of onset; GVHD grade according to the International Bone Marrow Transplant Registry severity Index [22]; presence of infections; presence of donor specific antibodies; posttransplant treatments and date (e.g., donor lymphocyte infusion, stem cell boost, growth factors; infusion of antiviral T cells); GVHD prophylaxis.

Information about TA-TMA will be collected including date of diagnosis (defined as the earliest date when all required laboratory criteria outlined in Inclusion Criterion #3 are met); diagnostic laboratory markers; initial management; and presence of signs and symptoms of end organ injury.

Baseline end organ injury will be evaluated as follows, with associated medications:

Confidential Page 46 of 89

- a. Kidney: doubling of serum creatinine compared with pre-HSCT level or patient receiving renal replacement therapy or proteinuria ≥ 30 mg/dL OR rUPCR ≥ 1 mg/mg.
- b. Lungs: hypoxemia or any need for noninvasive or invasive positive pressure ventilation.
- c. Cardiovascular: pulmonary hypertension diagnosed by a cardiologist using cardiac catheterization, or pulmonary hypertension criteria on echocardiography or arterial hypertension, defined by systolic BP  $\geq$  140 mmHg and/or diastolic BP  $\geq$  90 mmHg at baseline or hypertension requiring > 2 medications (excluding diuretics).
- d. Serositis: clinically significant pleural effusion or pericardial effusion requiring surgical therapy (e.g., pericardiocentesis/ thoracocentesis).
- e. CNS: seizures attributable to posterior reversible encephalopathy syndrome.

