## 6.5.7 Efficacy assessments

#### 6.5.7.1 Clinical response

Clinical response is defined as an improvement in laboratory markers and, in patients with signs or symptoms of organ dysfunction at baseline, also as an improvement in clinical status (see Section 5.2.1).

To assess laboratory improvement, LDH and platelets count will be collected at baseline and at each time point of clinical response evaluation.

To assess the clinical status, the following clinical and laboratory parameters will be collected at baseline and at each time point of clinical response evaluation:

- Creatinine; presence of renal replacement therapy (including start date, end date and reason).
- Presence of noninvasive or invasive positive pressure ventilation or oxygen, including start date, stop date and reason.
- Presence of nausea, vomiting or anorexia including attributed reason.
- Stool output/day (reported either as number of episodes or mL).
- Neurological status (e.g. presence of seizures, mental alteration, stability of irreversible neurological conditions) including attributed reason.
- Presence of pulmonary hypertension and related medications.
- Systolic and diastolic BP and anti-hypertensive medications excluding diuretics.
- Presence of pericardial or pleural effusion requiring pericardiocentesis or thoracocentesis including attributed reason.

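### The creatinine branches of renal response do not require the patient to be off renal replacement therapy, so a dialysis-lowered creatinine can score as a renal response

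*SAP*

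**What the plan says.** Protocol 5.2.1 gives the renal criterion as a list of alternatives: "Renal response requires > 40 % reduction in creatinine, or normalization of creatinine, or discontinuation of renal replacement therapy", with a fall of at least 50% in rUPCR as the fourth. SAP 6.2 repeats the list and SAP Appendix I programs it.

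- **Entry to the renal rule:** "IF (Has the patient any sign/symptom of kidney dysfunction=Yes) THEN DO".
- **Creatinine reduction:** "creatinine_baseline - creatinine)/creatinine_baseline) > 0.4".
- **Creatinine normalization:** "creatinine_baseline > ULN mg/dL (abnormal high)) AND (creatinine <= ULN mg/dL (normal".
- **RRT:** "discontinuation of renal replacement therapy=Yes". This is sufficient on its own and places no condition on the other branches.
- **rUPCR:** a relative fall from baseline of at least 0.5.

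Clinical response then needs the laboratory markers (LDH and platelets), at least one organ criterion, no TA-TMA-attributable deterioration in other organs, and no prohibited medication.

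RRT appears in two other relevant places. Protocol 6.1.2.1 lists it among the kidney injuries that count towards clinical worsening: "requirement of renal replacement therapy after initial TA-TMA control, sustained (> 7 days) and attributable to TA-TMA". Protocol 6.5.7.1 has it recorded at baseline and at each response evaluation: "Creatinine; presence of renal replacement therapy (including start date, end date and reason".

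**The concern.** Dialysis removes creatinine from the blood. This is general knowledge and is not stated in the documents. A creatinine value taken on RRT therefore reflects the machine as well as the kidney, and a fall in it need not mean renal recovery.

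The plan guards comparable criteria against supportive treatment. Platelets count only without transfusion in the preceding 7 days, pulmonary response requires positive pressure ventilation to have stopped, and control of hypertension caps the number of drugs. The plan also treats stopping RRT as a renal response. The creatinine branches have no matching guard.

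What is at stake is the derived clinical response, at Week 24 and wherever else the same derivation is used: Week 12 response, time to response and duration of response. The trial has 12 patients and its efficacy findings are meant to inform further development, so one misclassified patient would be visible in the rate.

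**Working it through.** **1. The plan's own figure.** SAP Section 5 gives a 72% probability of at least 8 responders among 12 if the true rate is 70%. The exact binomial gives P(X ≥ 8 | n = 12, p = 0.70) = 0.7237, so the figure reproduces. The present point does not depend on it.

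**2. Does the renal rule fire on RRT?** I read the four conditions as alternatives, as Protocol 5.2.1 words them, and applied the rule to hypothetical patients. The values are assumptions: kidney dysfunction at baseline = Yes, ULN 1.2 mg/dL, rUPCR unchanged, RRT not discontinued.

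| Patient | Baseline creatinine (mg/dL) | Visit creatinine (mg/dL) | Check | Score as written | Score with an off-RRT condition |
|---|---|---|---|---|---|
| Starts RRT on study | 4.0 | 2.0 | (4.0 − 2.0)/4.0 = 50% > 40% | 1 | 0 |
| Starts RRT on study | 1.8 | 1.1 | 1.8 > 1.2 and 1.1 ≤ 1.2 | 1 | 0 |
| On RRT at baseline and still on it | 3.0 | 1.7 | (3.0 − 1.7)/3.0 = 43% > 40% | 1 | 0 |
| Kidney function worsens, no RRT | 4.0 | 6.0 | creatinine rises | 0 | 0 |

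The first and last rows start from the same baseline. The patient who goes on to RRT can score a renal response, while the patient who worsens without it cannot.

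**3. Does another rule catch it?**

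- *Deterioration and new-organ clauses.* These cover organs other than those involved at baseline. The renal rule is entered only if the kidney was involved at baseline, so new RRT is never a new organ for these patients. By the definition in Protocol 6.5.1 ("Kidney: doubling of serum creatinine compared with pre-HSCT level or patient receiving renal replacement therapy or proteinuria" at or above a threshold, or rUPCR ≥ 1 mg/mg), inclusion criterion 5 gives every eligible patient kidney involvement.
- *Intercurrent events.* Protocol 8.3.4.2 names prohibited medication and study withdrawal. Starting RRT is neither.
- *Clinical worsening.* It needs active laboratory TA-TMA and three of five organ injuries, and it is not a term in the derived response.

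No rule closes the gap.

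**4. Effect on the rate.** For the patient's status to change, three things must hold together: RRT produces a qualifying creatinine, the LDH and platelet criteria are met, and no other organ criterion is met. If k of 12 patients fit that description, the rate is inflated by k/12. The documents do not give k, so I show a range starting from 8 scored responders. The 95% Clopper-Pearson limits for x responders of n are Beta(0.025; x, n − x + 1) and Beta(0.975; x + 1, n − x).

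| k (assumed) | Responders after correction | Rate | 95% CI |
|---|---|---|---|
| 0 | 8/12 | 66.7% | 34.9 to 90.1 |
| 1 | 7/12 | 58.3% | 27.7 to 84.8 |
| 2 | 6/12 | 50.0% | 21.1 to 78.9 |

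Each such patient is worth 1/12 = 8.3 points.

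**The case against.** The strongest reply is that the gap is real in the text but narrow in effect. Several parts of that reply stand.

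- **The creatinine branches are not easily met.** Normalization also needs a baseline above ULN, so a patient who entered on proteinuria with normal creatinine cannot use it. The 40% fall is measured from baseline, not from an on-study peak, so a patient whose kidneys fail later must be dialysed well below the pre-failure value.
- **Other criteria may already qualify the patient.** A fall in rUPCR, freedom from transfusion or a cardiovascular response is enough. Appendix I counts any transfusion before first dose as baseline transfusion, so freedom from transfusion could often be available. A reader might infer that every patient with dialysis-lowered creatinine adds 8.3 points. The documents do not support that.
- **There is no contradiction with clinical worsening.** A reader might infer that one patient could be both worsened and a responder at the same evaluation. Worsening requires active laboratory TA-TMA, which includes LDH above 1.5 x ULN, and response requires LDH below 1.5 x ULN.
- **8/12 is not a success threshold.** The sample size is described as practical and no hypothesis is tested.
- **The SAP follows the protocol.** This is a gap in the endpoint definition, not a programming error.

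It is also true that investigator-assessed response is summarized by visit and that all data are listed, so with 12 patients a case could be spotted. That would reveal a misclassification but would not correct the derived endpoint or its confidence interval.

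**Conclusion.** The point holds in limited form. As written, both creatinine branches can score a renal response in a patient who is on RRT when creatinine is measured, whether RRT began on study or continued from baseline, and nothing else in the derivation prevents it. The effect on clinical response is 8.3 points per patient, but only for a patient who also meets the LDH and platelet criteria and meets no other organ criterion.

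This rests on two assumptions from outside the documents: that dialysis lowers measured creatinine, and that at least one such patient occurs. The number is unknown and may be zero. TMA response does not use creatinine and is unaffected. The point is worth settling before the endpoint is derived, because the direction of error is known (upward) and the remedy is small.

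**What to change.** In the Appendix I derivation, set both creatinine branches to not met when the patient is on RRT at the creatinine sample or within a pre-stated look-back before it. Seven days would match the transfusion rule. If the sponsor prefers another window, it should be fixed in advance and justified. The RRT start and end dates needed are already collected under Protocol 6.5.7.1.

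Record the change in SAP Section 10 as a departure from the definition in Protocol 5.2.1, and report the response rate under the rule as it now stands as a sensitivity summary. The SAP should also state how rUPCR is scored while a patient is on RRT. The change above does not touch that branch or the non-renal criteria, so a patient on RRT could still count as a clinical responder through them.

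The programming cost is one added condition on two branches. The response rate may be slightly lower. The endpoint definition also changes late in an open-label study: SAP Section 10 already describes recruitment in the past tense. That is why both versions should be shown. The change concerns endpoint scoring only and has no bearing on how patients are managed.

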8.7.2 MEDICAL HISTORY AND CURRENT MEDICAL CONDITIONS

Medical history (conditions that ended before the date of enrollment) and current medical conditions (those that started before and were ongoing at the date of enrollment) will be coded using the Medical Dictionary for Regulatory Activities (MedDRA) version current at the time of DBL and tabulated by System Organ Class (SOC) and Preferred Term (PT).

Baseline TA-TMA data will be summarized using the following variables:

- The platelet value at the diagnosis (10^9/L),
- The highest platelet value achieved after transplant (10^9/L),
- The LDH value at diagnosis (U/L),
- Diagnosis of TA-TMA established as per laboratory/clinical markers indicating TMA.
 - o Presence of schistocytes in the peripheral blood smear (yes or no),
 - Absolute number of schistocytes per high power field in the peripheral blood smear (per hpf),
 - o Was any biopsy performed to confirm the histologic diagnosis of TA-TMA (yes or no),
 - If yes, sample location,
 - o De novo anemia at diagnosis (yes or no)
 - The most recent pre-transfusion hemoglobin (Hb) level at diagnosis (g/dL),
 - Proteinuria at diagnosis (yes or no),

Page 21 of 39

- The most recent rUPCR value at diagnosis (mg/mg).
- The most recent proteinuria value at diagnosis (mg/dL),
- Elevated plasma concentration of Sc5b-9 above ULN (yes or no),
 - Sc5b-9 level at diagnosis (ng/mL),
- Arterial hypertension defined by systolic blood pressure (BP) ≥ 140 mmHg and/or diastolic BP ≥ 90 mmHg (yes or no),
 - The pre-antihypertensive therapy systolic blood pressure (mmHg),
 - The pre-antihypertensive therapy diastolic blood pressure (mmHg),
 - Patients taking any antihypertension medication (yes or no),
 - Number of ongoing medications, excluding diuretics,
 - 0 medication,
 - ≤ 2 medications,
 - > 2 medications,
- o Time between HSCT and TA-TMA diagnosis (days),
- o Time between TA-TMA diagnosis and study enrollment (days).
- o TA-TMA persisting despite initial management of any triggering condition (yes or no),
- o Any sign/symptom of kidney dysfunction (yes or no),
 - The most recent serum creatinine value (mg/dL),
 - The last serum creatinine value pre-transplant (mg/dL),
 - Patients requiring renal replacement therapy (yes or no),
- Any sign/symptom of lungs dysfunction (yes or no),
 - The lowest oxygen level in the blood (%),
 - Patients receiving noninvasive positive pressure ventilation (yes or no),

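### The dialysis branch of renal response does not require dialysis at baseline, so stopping dialysis that began on study can be scored as renal improvement

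*SAP*

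**What the plan says.** Clinical response needs the laboratory markers plus at least one organ criterion in patients with organ dysfunction at baseline. SAP 6.2 refers to Appendix I for the exact derivation.

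- **Renal block, SAP Appendix I.** It opens with "IF (Has the patient any sign/symptom of kidney dysfunction=Yes) THEN DO". One of its four alternatives is "discontinuation of renal replacement therapy=Yes". No line in the block refers to RRT status at baseline or to when RRT started.
- **Protocol 5.2.1.** The renal criterion lists the same alternative without restriction: "or normalization of creatinine, or discontinuation of renal replacement therapy, or" the rUPCR reduction. SAP 6.2 repeats this. The criteria are tied to baseline by organ: "depending on the organ/system involved at baseline as described in Section 6.5.1".
- **Baseline kidney injury, protocol 6.5.1(a).** RRT is one of several alternatives. An rUPCR of at least 1 mg/mg is enough without dialysis, and Inclusion Criterion 5 requires that value of every patient.
- **Clinical worsening, protocol 6.1.2.1.** The kidney item is "requirement of renal replacement therapy after initial TA-TMA control, sustained (> 7 days) and attributable to TA-TMA".
- **Data collected.** SAP 8.7.2 lists RRT need at baseline as a yes/no item. Protocol 6.5.7.1 collects RRT at baseline and at each response evaluation, with start date, end date and reason.

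**The concern.** A component meant to capture improvement should compare the patient with his or her own baseline. Stopping RRT does so only if RRT was in use at baseline. If RRT begins after the first dose and is later stopped, the patient has had a kidney deterioration followed by some recovery, and may end no better than at entry or worse. The branch does not separate the two courses.

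One organ component is enough for the clinical status part of clinical response, so this branch alone can supply it. The same derivation feeds response at Week 12 and Week 24, response by visit, and time to and duration of clinical response. With 12 patients, a single classification is visible in the result.

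**Working it through.** **1. The plan's own figure.** Protocol 8.1 and SAP 5 give a 72% probability of at least 8 responders among 12 at a true rate of 70%. The exact binomial sum over k = 8 to 12 of C(12,k) × 0.7^k × 0.3^(12−k) is 0.7237. The figure is reproduced, and this point does not alter it.

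**2. Who passes the kidney gate.** Inclusion Criterion 5 requires rUPCR ≥ 1 mg/mg, and protocol 6.5.1(a) counts rUPCR ≥ 1 mg/mg as baseline kidney injury. Every eligible patient therefore passes, dialysed or not, if the form item behind the gate follows 6.5.1.

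**3. A test patient (all values assumed).** Kidney dysfunction at baseline, no RRT at baseline, RRT started and stopped on study, discontinuation item recorded as Yes at the visit. Creatinine goes from 1.8 to 2.4 mg/dL (ULN 1.2) and rUPCR from 2.0 to 2.2 mg/mg. The four branches are joined by OR, as in the protocol; some connectors are missing from the SAP text as extracted.

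- Creatinine reduction: (1.8 − 2.4)/1.8 = −0.33, not above 0.4. Fails.
- Creatinine normalization: baseline 1.8 > 1.2, but 2.4 is not ≤ 1.2. Fails.
- rUPCR reduction: (2.0 − 2.2)/2.0 = −0.10, not ≥ 0.5. Fails.
- RRT discontinuation: Yes. Passes.

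| Patient (same laboratory values) | Rule as written | With baseline RRT required |
|---|---|---|
| RRT started and stopped on study | 1 | 0 |
| On RRT at baseline, then stopped | 1 | 1 |
| Never on RRT | 0 | 0 |

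As written, the patient who needed dialysis on study scores 1 and the otherwise identical patient who never needed it scores 0.

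**4. Whether another clause stops it.** The deterioration clause in Appendix I concerns other organs, so it does not cover the kidney in a patient with kidney involvement at baseline. The intercurrent events in protocol 8.3.4.2 and SAP 8.8.2.2 are prohibited medication and study withdrawal; starting RRT is neither. Clinical worsening is not a term in the derivation.

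**5. How the other components are written.** In Appendix I, freedom from transfusion is scored only if transfusions were given at baseline. Serositis requires the effusion and the surgical therapy at baseline. The cardiovascular rule requires pulmonary hypertension, or raised blood pressure or more than 2 antihypertensives, at baseline. The RRT branch has no such condition.

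**6. Size.** The branch changes clinical response only when all of these hold:

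- the LDH and platelet criteria are met;
- no other renal branch and no other organ component is met;
- no other organ has deteriorated;
- no prohibited medication has been used.

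One such patient is 1/12 = 8.3 percentage points. For example, 7/12 = 58.3% (Clopper-Pearson 95% CI 27.7 to 84.8) becomes 8/12 = 66.7% (34.9 to 90.1). The documents give no rate of RRT begun on study, so an expected number cannot be computed.

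**The case against.** The strongest reply is that the outcome depends on a form that is not in the documents. The discontinuation item appears to come from the response evaluation form. Its completion instruction, answer options and time reference are not given, and it may be open only to patients on RRT at baseline. The kidney gate is a form item too. This stands: the documents show that the stated rule does not exclude the misclassification, not that it will occur. It does not remove the point, because neither document states the restriction and SAP 6.2 presents Appendix I as the exact rules.

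Four stronger readings are tempting and are not supported.

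- **That RRT stopped early in the study yields renal response at Week 24.** Response is evaluated visit by visit, and nothing says the item is still Yes many weeks after RRT ended.
- **That each such patient adds 8.3 points once LDH and platelets are met.** If any other organ component is met, the patient is a responder anyway and the effect is zero.
- **That a patient in protocol-defined clinical worsening is counted as a responder.** Sustained RRT attributable to TA-TMA is the kidney item, but 6.1.2.1 also needs active laboratory TA-TMA and 3 of 5 organ injuries. RRT alone does not meet it.
- **That a patient first dialysed on study should reach clinical response only through creatinine or rUPCR.** That holds for renal response; other organ components remain open.

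There are also partial safeguards. The endpoint is secondary and descriptive, investigator-assessed response is tabulated by visit, and all collected data are listed. A discordant case among 12 patients could be noticed, but the derived proportion would still count it.

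**Conclusion.** The point holds in a limited form. The RRT branch in SAP Appendix I, and the matching text in protocol 5.2.1 and SAP 6.2, can credit a patient with renal response for stopping RRT that was not in use at baseline, with creatinine and rUPCR unchanged or worse. This is a flaw in a stated rule rather than a missing detail, since the transfusion and serositis rules do code the specific baseline state.

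It rests on two assumptions about forms not in the documents: that the kidney dysfunction item follows protocol 6.5.1, and that the discontinuation item is not restricted to patients on RRT at baseline. The effect on clinical response is 8.3 percentage points for each patient in whom this branch is decisive, and zero otherwise. How many patients that would be is unknown. The plan should be corrected, but nothing here shows that the response rate is in fact inflated.

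**What to change.** In SAP Appendix I, replace the RRT branch with: (renal replacement therapy at baseline = Yes) AND (renal replacement therapy ongoing at the visit = No). The second condition also settles the time reference. State the same baseline condition in protocol 5.2.1 and SAP 6.2; the protocol synopsis repeats the wording and should follow.

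A patient on RRT at baseline who stops still scores as a renal responder. A patient first dialysed on study could then reach renal response only through the creatinine or rUPCR branches, with non-renal components unaffected.

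The cost is one coded condition plus matching text in both documents. Baseline RRT status and RRT dates are already collected. The response count may be slightly lower. SAP section 10 describes recruitment in the past tense, so the change would come late in an open-label study. It should be dated, explained and made before database lock.
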